5.5. Rationale for Study Design and Dose for Investigational Product

5.5.1. Rationale for Study Design

UDCA is widely accepted to be the first-line therapy for PBC. However, PBC may progress despite UDCA treatment, and UDCA is intolerable to a minority of patients. The 2017 EASL guidelines indicate that patients should continue to be evaluated for their risk of developing end-stage complications that may require treatments in addition to UDCA. For patients who respond to UDCA, an individualized approach is recommended, while the addition of second-line therapy is recommended for patients with an inadequate response to UDCA. Second-line therapy is specified as licensed OCA, off-label medications (e.g., fibrates, budesonide), and investigational treatments under evaluation in clinical trials ([EASL 2017](#)).

OCA is a selective FXR agonist that has been shown to affect significant reductions in ALP in patients with PBC who demonstrated no or partial response to UDCA. As such, OCA has been conditionally approved for patients with PBC in combination with UDCA for those with an inadequate response to UDCA or who are intolerant to UDCA.

A number of small studies and nonrandomized trials in PBC have suggested that fenofibrate or BZF in combination with UDCA may reduce ALP levels in non-or partial UDCA responders. In a prospective, double-blind randomized study, addition of 400 mg/day BZF in patients with PBC with inadequate biochemical response to UDCA was reported to improve pruritus, biochemical prognostic markers, and liver stiffness progression ([Corpechot 2018](#)). This study also provided important information concerning the safety profile of BZF when used longer term in patients with PBC.

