6.2. Efficacy Objectives

[figure not shown]
The efficacy objective is to assess the effects of the OCA + BZF FDC tablet in subjects with PBC on the following:

- Biochemical disease markers, including ALP, GGT, ALT, AST, and total and conjugated bilirubin
- ALP $<1.67\times$ ULN, total bilirubin \leq ULN, and ALP decrease of $\geq 15\%$ from baseline
- Noninvasive assessments of liver fibrosis (transient elastography [TE], enhanced liver fibrosis [ELF] score)
- Disease severity scores (GLOBE, UK-PBC, and model of end-stage liver disease [MELD])

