18. Treatment with the following medications 30 days before Day 1 of Study 977-311, or plans to use these medications during the study: azathioprine, colchicine, cyclosporine, methotrexate, mycophenolate mofetil, pentoxifylline, rifampicin, statins, budesonide and other systemic corticosteroids (short-term use up to 2 weeks is permitted), monoamine oxidase inhibitors (MAOIs), and potentially hepatotoxic drugs (including α -methyl-dopa, sodium valproic acid, isoniazid, and nitrofurantoin)
19. Treatment with the following medications within 12 months before Day 1 of Study 977-311, or plans to use these medications during the study: antibodies or immunotherapy directed against interleukins or other cytokines or chemokines
20. Participation in a study of another investigational medicine or device within 30 days before Day 1 of Study 977-311 (except for Study 747-213, Study 747-214, or other eligible Sponsor study)
21. History of or ongoing alcohol or drug abuse within 1 year before Day 1 of Study 977-311. Subjects with moderate alcohol use within 3 months prior to the last visit in parent study, before transitioning to Study 977-311, will be excluded from this study. Moderate alcohol consumption is defined as 1 standard drink per day for women and 2 drinks per day for men; whereby 1 standard drink is equivalent to: 12 oz beer (5% alcohol), 5 ounces of wine (12% alcohol), or 1.5 ounces of 80 proof (40% alcohol)
22. History of noncompliance with medical regimens, or is considered by the Principal Investigator not able to meet the requirements as specified in the protocol from Day 1 throughout the duration of the study
23. Blood or plasma donation within 30 days before Day 1
24. Mental illness or other condition which may impair decision making, such that the validity of informed consent or ability to be compliant with the study is uncertain
25. A CK value on Day 1 of Study 977-311 $\geq 5 \times$ ULN or any abnormal laboratory value that is considered CS in the opinion of the Principal Investigator and Sponsor at the last visit in parent study, before transitioning to Study 977-311
26. Known or suspected nephrotic syndrome in the last 30 days, before rolling over to this study, based on the following diagnostic criteria (both Type 1 and Type 2):
 - Proteinuria, spot urine protein: albumin/creatinine ratio (ACR) of >300 mg/mmol (subjects with normal renal function and ACR values analyzed to be below the lower limits of detection are permitted)

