8.4. Subject Withdrawal Criteria

Subjects who are discontinued from investigational product should be requested to continue with study visits until Month 60/EOS. Subjects who discontinue investigational product may be requested to come in for an Unscheduled Visit at the discretion of the Investigator depending on the timing of their next scheduled study visit.

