9.2. Concomitant Medications

Subjects must follow the medication restrictions outlined in the inclusion and exclusion criteria ([Section 8](#)) during the study.

Relevant information about all concomitant medications (including prescribed, over the counter, or herbal preparations) taken before (i.e., within 30 days of Day 1) and during the study must be recorded in the source documents and eCRF, as well as any dose or dose regimen changes that occur during the study. Note that on days when blood is drawn for PK sample, concomitant medications should be taken after the PK sample is taken (i.e., 6 hours post dosing).

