9.1. Efficacy Endpoints

The LTSE Population will be the population used for the efficacy analyses. Baseline is defined as the last assessment performed before the first dose of investigational product in Study 977-311, unless otherwise specified.

The efficacy endpoint at post-baseline site visits includes:

- Response rate of $\geq 40\%$ reduction from baseline and normalization rates of ALP
- Normalization rates of GGT, ALT, AST, total and conjugated bilirubin
- Change from baseline in GGT, ALT, ALP, AST, and total and conjugated bilirubin
- Percentage of subjects with ALP $< 1.67 \times \text{ULN}$, total bilirubin $\leq \text{ULN}$, and ALP decrease of $\geq 15\%$ from baseline
- Change from baseline in noninvasive markers of liver fibrosis, including liver stiffness measured by TE and ELF score
- Change from baseline in the GLOBE, UK-PBC, and MELD scores

All continuous and categorical additional endpoints will be summarized using descriptive statistics at baseline and at each scheduled post-baseline visit. No statistical inference will be done on those endpoints.

[figure not shown]
The intercurrent event in this study includes the use of prohibited medication and treatment discontinuation. Data collected after the intercurrent events, such as the use of prohibited medications, and data collected after treatment discontinuation will be included in the analyses (Treatment Policy Estimand).

The 5 attributes of the efficacy estimand are provided in Table 1.

[figure not shown]
Table 1: Attributes of Efficacy Estimand

[figure not shown]
Estimand Attribute	Elements
Population	All subjects with PBC who participated and are actively taking investigational product in Study 747-213 or Study 747-214 (or other Sponsor studies)
Treatment	OCA+BZF FDC Tablets
Efficacy Endpoint	All efficacy endpoints
Intercurrent Events	Use of Prohibited medication (Treatment Policy) Treatment Discontinuation (Treatment Policy)
Primary Efficacy Endpoint Population Level Summary	Descriptive summary in the target population

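### With treatment policy as the only efficacy estimand in a single-arm study, the late response rates mix the FDC with off-drug time and other second-line PBC therapy, so they cannot be read as FDC durability

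*SAP*

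**What the plan says.** Protocol 6.2 sets the aim: "The efficacy objective is to assess the effects of the OCA + BZF FDC tablet in subjects with PBC on the following", followed by biochemical markers, the ALP and bilirubin composite, fibrosis measures and severity scores.

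SAP 9.1 and Table 1 turn this into one estimand for all efficacy endpoints. The treatment attribute reads only "OCA+BZF FDC Tablets". On events: "The intercurrent event in this study includes the use of prohibited medication and treatment discontinuation". Both are handled by treatment policy, and "data collected after treatment discontinuation will be included in the analyses (Treatment Policy Estimand").

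Protocol 8.4 adds: "Subjects who are discontinued from investigational product should be requested to continue with study visits until Month 60/EOS". Protocol 15.7 likewise expects those who stop to stay in the study.

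On other drugs, Protocol 9.2 says "Subjects must follow the medication restrictions outlined in the inclusion and exclusion criteria". Exclusion 18 in Protocol 8.3 names "azathioprine, colchicine, cyclosporine, methotrexate, mycophenolate mofetil, pentoxifylline, rifampicin, statins, budesonide and other systemic corticosteroids", then MAOIs and an open-ended group of potentially hepatotoxic drugs. Exclusion 19 covers cytokine-directed antibodies and immunotherapy. Neither these nor Protocol 9.2.1 to 9.2.8 mention non-study OCA or a non-study fibrate as restricted. Protocol 5.5.1, summarising the European guideline, states: "Second-line therapy is specified as licensed OCA, off-label medications (e.g., fibrates, budesonide), and investigational treatments under evaluation in clinical trials".

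**The concern.** In a randomised trial, treatment policy compares two strategies, each including whatever follows the assigned drug. Here there is one arm. The same rule yields the response of everyone who once started the FDC, whatever they take later. That is a legitimate quantity, but it is not the effect of the tablet named in the objective.

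A subject who stops in year 1 can contribute ALP values for four more years. Those values may be taken on no second-line drug, on marketed OCA, or on an off-label fibrate. None of these states is separated from being on the FDC in any planned summary. The Month 24 to Month 60 normalisation rates will naturally be read as durability of the FDC, and the plan gives the reader no means of checking that reading.

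SAP 10.7 adds to this. As written, a concomitant medication is one begun before the first dose and continued after it. A second-line drug begun later fits neither the prior nor the concomitant definition and could be missing from the medication table, although Protocol 9.2 requires it in the eCRF.

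**Working it through.** The plan has no figure to reproduce: there is no hypothesis, the sample size is not calculated, and no stopping or switching rate is given. What follows is an illustration under stated assumptions.

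**Inputs**
- N = 133 (Protocol 7.2), taking all subjects as assessed at Month 60.
- d, the share who have stopped the FDC but still attend: assumed 10-40%.
- s, the share of those on another second-line drug: assumed 25-75%.
- r, ALP normalisation on that drug. The documents offer three stand-ins: 0/11 on OCA with UDCA and 4/9 on OCA, BZF and UDCA (both Protocol 5.5.1), and 31% on BZF with UDCA at 24 months (Protocol 5.4.2). The 31% is complete biochemical response, which is stricter than normal ALP alone.
- p, normalisation among those still on the FDC: assumed 50% where needed.

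**Step 1. Points of the Month 60 rate that come from other drugs = d × s × r**

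| d | s | Subjects on another drug (133 × d × s) | r = 0 | r = 31% | r = 4/9 |
|---|---|---|---|---|---|
| 10% | 25% | about 3 | 0 | 0.8 | 1.1 |
| 20% | 50% | about 13 | 0 | 3.1 | 4.4 |
| 30% | 50% | about 20 | 0 | 4.7 | 6.7 |
| 40% | 75% | about 40 | 0 | 9.3 | 13.3 |

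The range is 0 to 13.3 points. In the second row at r = 31%, that is 133 × 0.20 × 0.50 × 0.31 = 4.1 subjects.

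**Step 2. Direction**

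If untreated stoppers do not normalise, the treatment-policy rate is (1 − d)p + d·s·r. Subtracting p leaves d(s·r − p), which is positive only when s·r exceeds p. The largest s·r in the range is 0.75 × 4/9 = 33.3%. So at p = 50% the treatment-policy rate is below the on-FDC rate throughout; it could be above only if p were under 33.3%.

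- d = 20%, s = 50%, r = 31%: 0.80 × 50% + 3.1% = 43.1%, against 50% among those still on the FDC and 40.0% if only responders still on the FDC count. Of counted responders, 3.1/43.1 = 7% are on another drug.
- d = 40%, s = 75%, r = 4/9: 0.60 × 50% + 13.3% = 43.3%, of which 13.3/43.3 = 31% of responders are on another drug.

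Step 1 therefore measures how much of the reported rate is not due to the FDC. It does not measure the gap between the treatment-policy and on-FDC summaries, which can have either sign.

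**Step 3. Which endpoints are exposed**

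Normalisation does not depend on baseline, so a switcher can meet it. The 40% reduction and the composite with a 15% decrease are measured from the last value before the first dose in this study (SAP 9.1), in subjects already taking parent-study product (Protocol 8.2). A switcher is less likely to meet those. The Week 12 ALP reductions in Protocol 5.4.3 were measured from a different baseline and cannot be carried over.

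**The case against.** Several counter-arguments have force.

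- *A reader might infer that treatment policy inflates the FDC response.* The documents do not support that. Off-drug subjects who take nothing count mostly as non-responders, and at p = 50% every scenario above puts the treatment-policy rate below the on-FDC rate.
- *A reader might infer that the protocol permits these drugs, or extra OCA on top of the FDC.* It does not say so. Exclusion 18 ends in an open-ended group, and Protocol 5.6.2 tells investigators to keep OCA dosing consistent with the protocol regimen. But calling the drugs prohibited would change no efficacy number, since data after prohibited medication are also kept.
- *Switching may be uncommon.* The guideline text in Protocol 5.5.1 concerns inadequate response to UDCA, not stopping this combination. Some mandatory stops, for portal hypertension or decompensation (Protocol 7.4.3), fall under the OCA contraindications in Protocol 5.4.1 and Table 1. The switching rates used here have no source.
- *An on-FDC summary has its own bias.* It drops subjects stopped for hepatic events or related Grade 3 events, which is informative selection. This stands, and is why it should not replace treatment policy.
- *The stakes are limited.* Safety is primary, efficacy is descriptive, the strategy is stated openly, discontinuations with reasons are tabulated and efficacy values are listed by subject. This limits the severity but does not close the gap: no summary separates the three states.

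**Conclusion.** The point holds as a gap in attribution. One estimand keeps all post-discontinuation data, subjects are retained to Month 60, other second-line therapy is not named as an event, and there is neither a comparator nor an on-treatment summary. The late normalisation rates cannot be read as durability of the FDC.

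Its size is unknown from the documents. Under the assumptions above, about 0 to 13 points of the Month 60 ALP normalisation rate could come from other drugs; the zero end is as well supported as the upper end. Neither a net upward bias nor permission to switch is established. No test, error rate or primary analysis is affected. The change should be made, because it is cheap and bears directly on the stated efficacy objective.

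**What to change.** In the SAP:
- Add to Table 1, as a separate intercurrent event, the start of non-study second-line PBC therapy (OCA, any fibrate or other PPAR agonist), with its own stated strategy.
- Keep the treatment-policy summary. Beside it, for each efficacy endpoint, give a supplementary on-FDC summary using values up to the last FDC dose plus a fixed short window, or up to the start of such therapy if earlier. SAP 10.2.1 already uses a last-dose window, of 30 days, for TEAEs.
- At each visit, show the number still on the FDC and the number on other second-line therapy.
- Correct SAP 10.7 so that medications begun after the first dose count as concomitant.

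In the protocol, reconcile exclusion 18 and Section 9.2 with the objective by stating the status of non-study OCA and fibrates, both during and after investigational product. Which status is appropriate is for the sponsor's clinical team.

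The cost is SAP wording and a few descriptive tables from data already collected. The on-FDC summary rests on fewer subjects at late visits and carries survivor selection, which must be stated with the table.

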9.2. Exploratory Endpoints

– MELD score ≥ 15

- Time to first occurrence of each individual component of the composite event endpoint.

All continuous and categorical additional efficacy endpoints will be summarized using descriptive statistics at baseline and at each scheduled post-baseline visit. No statistical inference will be done on those endpoints.

Kaplan-Meier (KM) estimates will be calculated for all time to event endpoints. The quartiles, including the median time-to-event and their respective 2-sided 95% CIs, will be presented. KM estimates will be plotted as a “survival curve”.

For the additional endpoints, data collected after the intercurrent events, such as the use of prohibited medications, and data collected after treatment discontinuation will be included.

9.2.1.1. Child-Pugh

The Child-Pugh score (CPS) is calculated within EDC by adding the scores of the 5 factors and can range from 5-15. Child-Pugh class is either A (a score of 5-6), B (7-9), or C (10 or above). Each of the factors is outlined in Table 2.

Table 2: Child-Pugh Score

Factor	Units	Points		
		1	2	3
Serum bilirubin	μmol/L	<34	34-50	>50
	mg/dL	<2.0	2.0-3.0	>3.0
Serum albumin	g/L	>35	35-28	<28
	g/dL	>3.5	3.5-2.8	<2.8
Prothrombin time	Seconds prolonged	0-3	4-6	>6
	INR	<1.7	1.7-2.3	>2.3
Ascites		None	Mild	Moderate-Severe
Hepatic encephalopathy		No	Grade 1 or 2	Grade 3 or 4

The ascites and hepatic encephalopathy variables are based on the investigator's clinical assessment.

The CP score will be summarized in the same manner as described above for the MELD score.

Child-Pugh class will be presented in shift tables showing the shift from baseline to each scheduled post-baseline visit by the count and percentage of subjects within each shift classification.

Individual factors will be presented in a listing.

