Safety data, including SAEs, TEAEs, physical examinations, electrocardiograms (ECGs), vital signs, clinical laboratory assessments, and treatment discontinuations, will be assessed.

The incidence of TEAEs and SAEs will be tabulated by system organ class, preferred term, and severity.

Laboratory parameters and vital signs will be summarized (including Hy's law) using descriptive statistics at baseline (defined as the last assessment performed before the first dose of investigational product in Study 977-311) and at each scheduled post-baseline visit in Study 977-311. The change from baseline will also be summarized. ECGs will be summarized using frequency at each visit. The shift from baseline will also be summarized.

[figure not shown]
Analyses of Efficacy and Exploratory Endpoints:

The LTSE Population will be the population used for the efficacy and exploratory analyses. Baseline is defined as the last assessment performed before the first dose of investigational product in Study 977-311, unless otherwise specified.

[figure not shown]
The efficacy endpoint at post-baseline site visits includes:

- Response rate of $\geq 40\%$ reduction from baseline and normalization rates of ALP
- Normalization rates of GGT, ALT, AST, total and conjugated bilirubin
- Change from baseline in GGT, ALT, ALP, AST, and total and conjugated bilirubin
- Percentage of subjects with ALP $< 1.67 \times \text{ULN}$, total bilirubin $\leq \text{ULN}$, and ALP decrease of $\geq 15\%$ from baseline
- Change from baseline in noninvasive markers of liver fibrosis, including liver stiffness measured by TE and ELF score
- Change from baseline in the GLOBE, UK-PBC, and MELD scores

The exploratory endpoints at post-baseline site visits include:

- MELD score ≥ 15

- Time to first occurrence of each individual component of the composite event endpoint.

All continuous and categorical efficacy and exploratory endpoints will be summarized using descriptive statistics at baseline and at each scheduled post-baseline visit.

Additional details regarding the planned analyses, methods, and outputs for the study will be included in the Statistical Analysis Plan (SAP).

PK, PD and PK/PD Analyses

The PK Population will be the primary population used for the PK analyses. The PD population will be the primary population for PD analyses. For PK/PD analyses, subjects in both the PK population and the PD population for the PD endpoint of interest will be included in the analysis. [REDACTED]

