7.4. Monitoring and Management of Potential Hepatic Injury and/or Disease Progression

Given the chronic and progressive nature of PBC, it is important to monitor for potential hepatic injury, disease progression, and/or hepatic decompensation. CP and MELD scores will be reviewed at each visit where labs are drawn ([Section 7.4.4](#) and [Section 14.2.1](#)). CP Scores should only be applied in subjects who have evidence of cirrhosis or progression to cirrhosis based on criteria presented in [Section 7.4.4](#). In addition, AEs, signs and symptoms of potential hepatic injury or decompensation, and laboratory values will also be reviewed at regular intervals as described in [Section 7.1.3](#). Based on the assessments of signs and symptoms of hepatic injury and/or muscular injury and liver biochemistry ([Section 7.4.1](#) and [Section 7.4.2](#)), the investigational product (OCA + BZF) may be interrupted or discontinued per the criteria discussed in [Section 7.4.2](#) and [Section 7.4.3](#).

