7.4.4. Child-Pugh Score

CP Score (Pugh 1973, Lucey 1997) is calculated and reported within the electronic data capture (EDC) system based on data entered into the eCRF by adding the scores from the 5 factors outlined in Table 6 and can range from 5 to 15. The Investigator should ensure all lab data is entered into the eCRF. Although CP score calculation will automatically be computed in all subjects (at all times data is obtained for the eCRF), it should only be applied to subjects who meet the criteria for progression to cirrhosis (see Section 7.4.4.1). Dose adjustment or discontinuation should not be considered based solely on the CP score in subjects who do not meet criteria for presence of cirrhosis.

A total score of 5 to 6 is considered Class A; a score of 7 to 9 is Class B (moderate, significant functional compromise); and a score of 10 and above is Class C (severe, decompensated

disease). The calculation of the CP Score includes Investigator assessments of ascites and hepatic encephalopathy, which may be assessed during the AE review at the scheduled visits, as well as total bilirubin, serum albumin, and prothrombin time (PT), the data for which will be obtained from the central laboratory.

Table 6: Child-Pugh Scoring System

Factor	Units	Points		
		1	2	3
Serum bilirubin	μmol/L	<34	34-50	>50
	mg/dL	<2.0	2.0-3.0	>3.0
Serum albumin	g/L	>35	28-35	<28
	g/dL	>3.5	2.8-3.5	<2.8
Prothrombin time	Seconds prolonged	0-3	4-6	>6
	INR	<1.7	1.7-2.3	>2.3
Ascites		None	Mild	Moderate-Severe
Hepatic encephalopathy ^a		No	Grade 1 or 2	Grade 3 or 4

CP=Child-Pugh; INR=international normalized ratio

The CP score is calculated by adding the scores for the 5 factors and can range from 5-15. CP class is either A (a score of 5-6), B (7-9), or C (10 or above). Decompensation indicates cirrhosis with a CP score of 7 or more (Class B).

^a Grade 0: normal consciousness, personality, neurological examination, electroencephalogram.

Grade 1: restless, sleep disturbed, irritable/agitated, tremor, impaired handwriting, 5 cps waves.

Grade 2: lethargic, time-disoriented, inappropriate, asterixis, ataxia, slow triphasic waves.

Grade 3: somnolent, stuporous, place-disoriented, hyperactive reflexes, rigidity, slower waves.

Grade 4: unrousable coma, no personality/behavior, decerebrate, slow 2-3 cps delta activity.

Child-Pugh criteria: (Pugh 1973, Lucey 1997, Vilstrup 2014).

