4. ANALYSIS POPULATIONS AND APPROACHES TO ANALYSIS

4.1. The LTSE Population

The LTSE Population will include all subjects who receive at least 1 dose of the FDC tablet.

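### The planned Child-Pugh tables take no visible account of cirrhosis status, so a Class B label in a subject without cirrhosis is counted together with decompensation

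*SAP*

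**What the plan says.** SAP 9.2.1.1 reproduces the five-factor scoring table and the class cut-offs (A 5-6, B 7-9, C 10 and above). It plans a score summary and, for class, states that "Child-Pugh class will be presented in shift tables showing the shift from baseline to each scheduled post-baseline visit", by count and percentage. The individual factors go into a listing. No cirrhosis condition appears in the section as published.

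The protocol is more restrictive. Section 7.4 says "CP Scores should only be applied in subjects who have evidence of cirrhosis or progression to cirrhosis". Section 7.4.4 separates calculation from use: "Although CP score calculation will automatically be computed in all subjects", but "it should only be applied to subjects who meet the criteria for progression to cirrhosis", with the criteria given in 7.4.4.1. The note to Table 6 defines decompensation as cirrhosis together with a score of at least 7.

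SAP 9.2.1.1 names no population. The protocol synopsis says "The LTSE Population will be the population used for the efficacy and exploratory analyses", and SAP 4.1 says "The LTSE Population will include all subjects who receive at least 1 dose of the FDC tablet". The SAP's safety analyses (Section 10) use the same population. SAP 7.1 and 7.2 list no cirrhosis variable at baseline, and SAP 9.5 and 10.8 plan no subgroup analyses.

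**The concern.** Long-term safety is the primary objective, and hepatic failure heads the protocol's list of OCA risks. A table of Child-Pugh class shifts is likely to be read as a record of hepatic worsening on treatment. Under the protocol's definition a score of 7 or more means decompensation only if cirrhosis is present, and the planned table does not carry that second condition.

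Two things follow. A Class B label produced by a laboratory value with another cause sits in the same cell as a decompensation. And the question a hepatologist would ask first, how often subjects with cirrhosis moved from A to B, cannot be answered from the tables because neither the numerator nor the denominator is separated out.

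**Working it through.** The plan states no figure of its own on this point, so the check is of the scoring rule and of what the planned outputs would show.

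**1. Can a subject without cirrhosis reach Class B?** Inputs: SAP Table 2 and protocol 7.4.4.1.

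- The minimum score is 5 × 1 = 5 and the maximum 5 × 3 = 15, as both documents say.
- One factor at 3 points and four at 1: 3 + 4 = 7, which is Class B.
- Three single-factor routes are purely laboratory: bilirubin above 3.0 mg/dL, albumin below 28 g/L, INR above 2.3. None alone satisfies 7.4.4.1, where laboratory findings count only in combination with platelets below 150,000/µL. Ascites is different: it is itself a cirrhosis indicator, absent acute liver failure.
- With no ascites and no encephalopathy there are 3³ = 27 laboratory point combinations. Those scoring below 7 have a laboratory sum of 3 (one combination) or 4 (three), so 27 − 4 = 23 score 7 or more, 19 of them in Class B. This counts routes; it is not a probability.

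**2. Is such a route realistic here?** Protocol 9.2.3 permits anticoagulants with monitoring and notes that BZF may strengthen coumarin-type agents. INR above 1.7 is an exclusion, so this route concerns rises after entry. The protocol guards against the artefact elsewhere: 7.4.4.1 discounts INR elevation due to antithrombotic drugs, and 14.2.1 accepts MELD ≥15 as an outcome only with an indication of cirrhosis and after other causes, including medication, are ruled out. SAP 9.2.1.1 shows no equivalent.

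**3. What would the table look like at baseline?** A score of 7 or more is excluded at entry, so essentially every subject starts in Class A. The content of the table is therefore the count moving from A to B or C.

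**4. How far could the two denominators differ?** Let c be the cirrhotic share, and p1 and p0 the Class B rates with and without cirrhosis. The all-subject rate is c·p1 + (1 − c)·p0. It is below p1 whenever p0 < p1. The study's value of c is not given. The only share in the documents, 22%, is from a different, retrospective cohort (protocol 5.5.1); 5% and 10% are assumptions. With N = 133, one shift in a cirrhotic subject and none elsewhere (p0 = 0):

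| Assumed c | n cirrhotic | 1/n | 1/133 | 133/n |
|---|---|---|---|---|
| 5% | 7 | 14.3% | 0.8% | 19.0 |
| 10% | 13 | 7.7% | 0.8% | 10.2 |
| 22% | 29 | 3.4% | 0.8% | 4.6 |

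If two subjects without cirrhosis also score Class B, the all-subject figure becomes 3/133 = 2.3%, and 2/3 = 67% of the Class B subjects are not decompensated by the protocol's definition. With six shifts among 29 cirrhotic subjects and the same two others, it is 8/133 = 6.0%, with 2/8 = 25%.

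The two effects pull in opposite directions: labels in subjects without cirrhosis add to the count, and the larger denominator lowers the percentage.

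**The case against.** The case for leaving the table alone has real substance.

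- *What the protocol limits.* Both restricting sentences sit in the section on monitoring and management. In 7.4.4 the next sentence concerns dose adjustment and discontinuation, so the limit may be on clinical action and not on tabulation. The protocol also uses a score of 7 or more without stating a cirrhosis condition, in exclusion criterion 3 and in Table 5. A reader might infer that the SAP flatly contradicts the protocol; the documents do not go that far. What stands is that the Table 6 note gives a score of 7 or more its meaning only with cirrhosis.
- *Missing text.* SAP numbering jumps from 9.2 to 9.2.1.1, and the section refers back to a MELD method that is not visible. A population statement may have been removed from the published copy. Hence the wording here: no visible reference.
- *The denominator.* Frequency among all treated subjects is a legitimate safety summary when the objective concerns subjects with PBC. A reader might infer from the table above that the plan understates risk 5- to 20-fold. The two rates answer different questions, the shares are assumed, and under SAP Section 5 the denominator at later visits would be the non-missing subjects, not 133.
- *Other safeguards.* Suspected liver-related outcomes are adjudicated independently, and the factor listing lets a careful reader find an albumin-only or INR-only Class B. That helps case by case. It does not give a rate by cirrhosis status.

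**Conclusion.** The point holds as a gap in presentation. As published, the Child-Pugh tables mix scores of 7 or more with and without cirrhosis, and no planned summary lets the reader separate them or see the rate among cirrhotic subjects. That Class B is reachable without any 7.4.4.1 indicator follows directly from the scoring table. That the tables cover all dosed subjects is inferred from the default population.

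The size is unknown. It depends on the cirrhotic share, which the documents do not give, and on how often subjects without cirrhosis score 7 or more. The net direction of the effect on the all-subject percentage is not fixed either. The tables are descriptive, Child-Pugh is not a listed efficacy endpoint, and no test is affected.

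A reader might conclude that the table should be confined to subjects cirrhotic at baseline or by each visit. That would be worse. The 7.4.4.1 criteria overlap the Child-Pugh factors, so entry to the table would depend partly on worsening. A subject without recognised cirrhosis but with a marked bilirubin rise would also drop out of a hepatic safety table into a listing.

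**What to change.** In SAP 9.2.1.1:

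1. Keep the all-subject score summary and class shift table, name the population, and label the table as computed regardless of cirrhosis.
2. Add the same shift table split by baseline cirrhosis status under protocol 7.4.4.1 (yes, no, not determinable), with n at each visit. Using baseline status keeps the strata free of post-baseline worsening.
3. Flag every post-baseline score of 7 or more with the factor or factors driving it and whether 7.4.4.1 was met by that visit. This captures progression to cirrhosis on study, and it identifies a drug-related INR rise in a subject who does have cirrhosis, which the split alone would not.
4. State the rule for assigning not determinable, and add cirrhosis status to the baseline disease characteristics in SAP 7.2.

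The cost is one derived flag and one additional table. The cirrhotic stratum will probably be small. Some status will stay undetermined: transient elastography is done only at qualified sites, the visible visit schedule has no biopsy, endoscopy or imaging, and the entry criteria already remove most subjects who would qualify through varices, ascites or low platelets.
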